### 7.8.2 Data Sets

The analyses of quality of life data will be restricted to randomized patients who have completed the quality of life questionnaire at baseline and on days 30 or 90.

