10.0 CRITERIA FOR MEASUREMENT OF STUDY ENDPOINTS

10.1 Definitions

10.1.1 Evaluable for adverse events. All patients will be evaluable for adverse event evaluation from the time of randomization.

10.1.2 Evaluable for BPI response. All patients who have completed a baseline and 30 days follow-up BPI will be considered evaluable for the primary endpoint. Patients who complete a baseline and a day 90 follow-up BPI will be considered evaluable for secondary BPI endpoints. Patients from Arm 1 who cross over to Arm 2 after their day 30 assessment are evaluable for BPI response from day 30 to day 90, if they have completed their day 30 and day 90 BPI.

10.1.3 Evaluable for quality of life assessment. All patients who have completed the quality of life questionnaire at baseline and on days 30 and 90 are evaluable for the quality of life endpoint.

10.1.4 Evaluable for change in opioid analysis. All patients who have completed Pain/Discomfort and Medication Questionnaires at baseline and within 24 hours of the 30 day visit are eligible for assessment. Only analgesic use in the past 24 hours will be recorded to increase compliance. If the patient is too unwell to visit the clinic, the Pain/Discomfort and Medication Questionnaire can be completed by the study nurse following a telephone call to the patient. Note: large fluctuations in opioid use are unlikely to occur due to intolerability of medications for many patients.

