14.2 Endpoints and Analysis

A stratified Cochran–Mantel–Haenszel (CMH) test adjusting for the stratification factor (HCC versus liver metastases) will be used to compare between two treatment arms for binary endpoints, such as proportion of patients with symptomatic HCC or liver metastases who report an improvement in pain/discomfort "intensity at worst" on BPI from baseline to day 30, proportion of patients with a clinically significant favourable change from baseline to day 30 and day 90 in other BPI scores, QoL on FACT-HBP, TOI and FACT-Hep and subscales, and proportion of patients with a 25% reduction in opioid use at 30 days. Primary analysis will include all patients who are assessed at both baseline and follow-up time of interest. Sensitivity analysis will also be performed by including those without assessment at specific follow-up time in the "no improvement" group. As cross-over of control patients to the RT Arm is permitted after day 30, after the primary endpoint (change in BPI on average) is assessed, the proportion of crossover patients who have RT at day 30 who have a subsequent clinically significant improvement in BPI at day 90 will be reported. The stratified logrank test will be used for time-to-event outcomes such as survival. A subgroup analysis will be performed based on the location of the metastases (HCC versus liver).

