### **6. Data Set Descriptions**

Two types of analysis samples will be used:

All Randomized Patients:

All patients who have been randomized in the study with the treatment arm being as randomized.

All Treated Patients:

All patients who are randomized to RT+BSC arm and have received a single 8 Gy dose of RT and all patients who are randomized to BSC arm.

All Day 30 BPI Response Evaluable Patients:

All patients who have completed a baseline and 30 days follow-up BPI.

All Day 90 BPI Response Evaluable Patients:

All patients who have completed a baseline and a day 90 follow-up BPI.

All BPI Response from Day 30 to Day 90 Evaluable Patients:

All patients who have randomized to BSC arm and crossed over to RT+BSC arm after their day 30 assessment and also completed their day 30 and day 90 BPI.

All QoL (quality of life) Evaluable Patients:

All patients who have completed the quality of life questionnaire at baseline and on days 30 and 90.

All Change in Opioid Evaluable Patients:

All patients who have completed Pain/Discomfort and Medication Questionnaires at baseline and within 24 hours of the 30 day visit.

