**Table 41: Proportion of Patients with Clinically Significant Improvement in QoL**

	RT+BSC N (%)	BSC N (%)	CMH P-value (*)
Patients with QoL at baseline and day 30			
With Clinically significant improvement (**) in QoL	**	**	**
≥5 point change in FACT-HBS	** (**, **)	** (**, **)	0.***
≥5 point change in FACT-TOI	** (**, **)	** (**, **)	0.***
With Clinically significant improvement (**) in QoL	** (**, **)	** (**, **)	0.***
≥5 point change in FACT-HBS	** (**, **)	** (**, **)	0.***
≥5 point change in FACT-TOI	** (**, **)	** (**, **)	0.***
Patients with QoL at baseline and day 90			
With Clinically significant improvement (**) in QoL	**	**	
≥5 point change in FACT-HBS	** (**, **)	** (**, **)	0.***
≥5 point change in FACT-TOI	** (**, **)	** (**, **)	0.***

\* Stratified Cochran-Mantel-Haenszel test adjusting for the stratification factor (HCC versus liver metastases)

\*\* ≥5 point change in both FACT-HBS and FACT-TOI

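### The named QoL analysis set (forms at baseline, day 30 and day 90) contradicts SAP 7.8.2, SAP Table 41 and Protocol 14.2, and nothing says which rule governs

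*SAP*

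**What the plan says.** Five places bear on who enters the QoL analysis.

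- **Protocol 10.1.3** counts as evaluable those who "completed the quality of life questionnaire at baseline and on days 30 and 90 are evaluable for the quality of life endpoint".
- **SAP section 6** repeats this for its one named QoL set: "All patients who have completed the quality of life questionnaire at baseline and on days 30 and 90".
- **SAP 7.8.2**, the data-set paragraph inside the QoL section, confines the analyses to those randomized who "completed the quality of life questionnaire at baseline and on days 30 or 90".
- **SAP Table 41**, the output for the QoL responder endpoint, has separate blocks headed "Patients with QoL at baseline and day 30" and "Patients with QoL at baseline and day 90".
- **Protocol 14.2**, in a paragraph on binary endpoints that names the QoL endpoints, states: "Primary analysis will include all patients who are assessed at both baseline and follow-up time of interest".

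QoL improvement is a secondary endpoint, compared between arms separately at day 30 and day 90 (SAP 4.2 and 7.8.5). Under Protocol 8.2.7, patients on best supportive care alone may receive radiotherapy once the day-30 assessment is done.

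**The concern.** The three rules give different denominators for the same table. Under the literal wording of the named set, a patient with valid baseline and day-30 forms leaves the day-30 comparison if the day-90 form is missing. In an end-stage population that form will often be missing because of death or decline. Membership of the day-30 analysis would then depend on something that happens up to two months after the outcome was measured.

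Day 30 is the only QoL comparison made before planned crossover. Completion of the day-90 form could differ by arm, and radiotherapy given to control patients after day 30 could itself influence it. The literal set could therefore distort the comparison as well as shrink it. The trial is open-label, so leaving the denominator open also leaves room to settle it after results by arm are known.

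**Working it through.** **No figure to reproduce.** The documents give no QoL sample size, power, FACT-Hep completion count or day-90 retention. The check is therefore a comparison of texts, followed by an illustration on stated assumptions.

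**Step 1: apply each rule to three patterns of completed forms.**

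| Rule | Baseline, day 30 and day 90 | Baseline and day 30 only | Baseline and day 90 only |
|---|---|---|---|
| Protocol 10.1.3 and SAP 6, literal | In, both visits | Out of both visits | Out of both visits |
| SAP 7.8.2 | In | In | In, but visit not specified |
| SAP Table 41 and Protocol 14.2 | In, both visits | In at day 30 | In at day 90 |

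The literal set and the per-visit rule disagree on the second and third patterns. SAP 7.8.2 admits both patterns but does not say who is counted at which visit. Taken alone, it would not stop a patient with only a day-90 form from sitting in the day-30 denominator.

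**Step 2: is the literal reading fair?** SAP section 6 and Protocol 10.1.2 define BPI evaluability separately for day 30 and day 90. QoL, next to it, gets one combined definition. A programmer following the named set would have reason to require all three forms.

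**Step 3: is the named set used?** Neither SAP 7.8 nor Tables 38 to 41 refers to it by name. Those tables carry no data-set label, whereas Tables 1 to 16 do. Table 40 has its own N row at each visit, which fits visit-specific denominators.

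**Step 4: illustration of lost patients.** SAP 2.3 reports 42 evaluable patients out of 66 randomized. Take 42 as a stand-in for day-30 FACT-Hep completers, and let r be the assumed share who also complete day 90. The literal set keeps 42 × r:

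| r (assumed) | Kept | Dropped from day 30 |
|---|---|---|
| 0.4 | 17 | 25 |
| 0.6 | 25 | 17 |
| 0.8 | 34 | 8 |
| 0.9 | 38 | 4 |

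The share dropped is simply 1 − r, so the table restates its assumption. The base is weak too, because 42 is a BPI count. Protocol 9.0 lets staff complete the pain questionnaire by telephone but not FACT-Hep (Appendix IX is more permissive), and 5.1.13 admits patients who cannot complete the QoL forms.

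**Step 5: illustration of selection.** Let p be the true day-30 improvement rate. Assume day-30 improvers return the day-90 form with probability 0.8 and non-improvers with probability 0.5, in both arms. The rate seen in the literal set is 0.8p / [0.8p + 0.5(1 − p)].

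- p = 0.29 (the pilot's FACT-HBS rate in Protocol 2.4): 0.232 / (0.232 + 0.355) = 0.395.
- p = 0.05 (borrowed from the BPI control rate in Protocol 14.3, as an assumption): 0.040 / (0.040 + 0.475) = 0.078.

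The difference moves from 24 points (29 − 5) to about 32 (39.5 − 7.8 = 31.7). With equal retention for improvers and non-improvers within each arm there would be no shift. Another retention pattern could reverse its direction. This shows only that the estimate can depend on which definition is used.

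**The case against.** The strongest reply is that the plan's operative text already points to a per-visit analysis. Protocol 14.2 states the rule in general terms, the Table 41 headings apply it, Table 40 has room for it, and SAP 7.8.2 is the more specific place within the QoL section. An analyst would have to disregard all of these to restrict the day-30 result to patients with day-90 forms. The phrase in SAP 6 and Protocol 10.1.3 can also be read as meaning each day respectively. SAP 7.8.3 refers to the two follow-up days in that sense when it sets compliance denominators.

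Much of this stands. A reader might infer that the day-30 QoL result will be a comparison among day-90 survivors, or that a particular share of day-30 data, such as 20 to 40%, will be lost. The documents support neither. The literal set is never invoked in the QoL analysis text or tables, and any such percentage is only an assumed retention rate turned round.

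The contradiction itself remains. The only named QoL set says something different from the analysis text, the same section splits BPI by visit, and no precedence is stated. The passages that favour a per-visit reading also show what the definition ought to say.

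**Conclusion.** The definitions conflict, and this rests on the wording alone. The named QoL set in SAP 6 and Protocol 10.1.3 is inconsistent with SAP 7.8.2, with SAP Table 41 and with Protocol 14.2. If it were followed literally, day-30 QoL would be limited to patients who also completed the day-90 form. That is a conditional risk of selection on a later outcome, and the per-visit reading is the likelier intent. The size cannot be computed from the documents, and the figures in the working are illustrations on assumed retention.

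The primary endpoint is untouched: it has its own day-30 BPI set in SAP 6. Only secondary QoL endpoints are affected. The correction should still be made, because a stated rule that would shrink and could bias the day-30 QoL result should not remain as the named definition.

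**What to change.** In SAP section 6, replace the single QoL set with two, mirroring the BPI sets, and use the same two in SAP 7.8.2:

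- **Day-30 QoL set:** randomized patients with FACT-Hep completed at baseline and day 30.
- **Day-90 QoL set:** randomized patients with FACT-Hep completed at baseline and day 90.

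State in the SAP that these supersede Protocol 10.1.3, and label Tables 40 and 41 with the set used at each visit. Table 41's headings already match, so there it is only a matter of naming the set. In the same edit, say whether the rule in Protocol 12.1, which makes patients given systemic therapy before the day-90 visit inevaluable for secondary endpoints, reaches back to day-30 QoL.

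The cost is a few lines of SAP text. No new data are needed. Accrual closed on June 2, 2022 (SAP 2.3), so a supersession statement in the SAP is enough and a protocol amendment would add little. The change should be dated before QoL results by arm are examined.

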### 7.8.3 Compliance

Compliance will be described, for each time of evaluation, by the number and percentage of subjects who filled out a questionnaire in that time of evaluation. The denominator used in calculating the percentage for baseline will be all randomized subjects who are required to complete the assessment. The denominator used for days 30 and 90 assessments will be the number of subjects known to be alive at days 30 or 90 and who are required to complete the assessments (**Table 38**).

### 7.8.4 Baseline and Change Score Analysis

Descriptive statistics (mean and standard deviation) for FACT-Hep questionnaire scores at baseline will be presented for each subscale and total scores. The same statistics will be generated for change scores from baseline to day 30 and day 90. The comparability of mean baseline scores and change scores at day 30 and day 90 between treatment groups will be assessed using a Wilcoxon rank sum test (**Table 39 and Table 40**).

### **7.8.5 Proportion of Patients with Clinically Significant Improvement in QOL**

A clinically significant improvement in QOL is defined by  $\geq 5$  points change in the Functional Assessment of Cancer Therapy (FACT) Hepatobiliary Subscale (FACT-HBS) and Trial Outcome Index (FACT-TOI) from baseline. Proportions of patients who had clinically significant improvement in QoL from baseline to day 30 and day 90 are summarized in **Table 41** and compared by a stratified CMH test adjusting for the stratification factor (HCC versus liver metastases) (**Table 41** ).

## 8. Appendices

### Appendix 1: Tables and Figure

**Table 1: Patient Disposition**

Data set: All Randomized Patients			
	Number of patients (%)		
	RT+BSC	BSC	Total
Randomized	N=**	N=**	N=**
Received RT	** (**)	NA 	NA 
Not received RT	** (**)	NA 	NA 
Reason for not received RT			
Progressive disease	** (**)	NA 	NA 
Intercurrent illness	** (**)	NA 	NA 
Patient refusal	** (**)	NA 	NA 
Adverse events	** (**)	NA 	NA 
Death	** (**)	NA 	NA 
Other	** (**)	NA 	NA 
Crossed over to RT	NA 	** (**)	NA 
Not crossed over to RT	NA 	** (**)	NA 
Reason for not crossed over to RT			
Progressive disease	NA 	** (**)	NA 
Intercurrent illness	NA 	** (**)	NA 
Patient refusal	NA 	** (**)	NA 
Adverse events	NA 	** (**)	NA 
Death	NA 	** (**)	NA 
Other	NA 	** (**)	NA 

 NA: Not Applicable

**Table 2: Follow-up of patients**

Data set: All Randomized Patients			
	Number of patients		
	RT+BSC N = **	BSC N = **	Total N = **
Number of patients alive	**	**	**
Follow-up (months)			
Median	**	**	**
Minimum-maximum	**_**	**_**	**_**

**Table 3: Accrual by Center**

[figure not shown]
Data set: All Randomized Patients			
	Number of patients (%)		
	RT+BSC N = **	BSC N = **	Total N = **
Center #1	** (**)	** (**)	** (**)
Center #2	** (**)	** (**)	** (**)
Center #3	** (**)	** (**)	** (**)
...	** (**)	** (**)	** (**)

**Table 4: Accrual by Stratification Factor (except center) at Randomization**

Data set: All Randomized Patients			
	Number of patients (%)		
	RT+BSC N = **	BSC N = **	Total N = **
Type of Liver Cancer			
HCC	** (**)	** (**)	** (**)
Liver metastases	** (**)	** (**)	** (**)

Source: CRF Eligibility Worksheet

**Figure 1: Accrual by Calendar Time**

**Table 5: Eligibility and Reasons for Ineligibility and Major Protocol Violations**

Data set: All Randomized Patients			
	Number of patients (%)		
	RT+BSC N = **	BSC N = **	Total N = **
Eligible	** (**)	** (**)	** (**)
Not Eligible	** (**)	** (**)	** (**)
Reason for ineligibility			
<Reason 1>	**	**	**
<Reason 2>	**	**	**
...	**	**	**
Major protocol violation			
<violation type 1>	**	**	**
<violation type 2>	**	**	**
...			

**Table 6: Pre-treatment Characteristics at Baseline**

Data set: All Randomized Patients			
	Number of patients (%)		
	RT+BSC N=**	BSC N=**	Total N=**
Gender			
Female	** (**)	** (**)	** (**)
Male	** (**)	** (**)	** (**)
Age (years)			
N	**	**	**
Median	**	**	**
Min - Max	** - **	** - **	** - **
< 65	** (**)	** (**)	** (**)
≥ 65	** (**)	** (**)	** (**)
ECOG Performance Status			
0	** (**)	** (**)	** (**)
1	** (**)	** (**)	** (**)
2	** (**)	** (**)	** (**)
3	** (**)	** (**)	** (**)
4	** (**)	** (**)	** (**)
BMI (kg/m  )			
N	**	**	**
Median	**	**	**
Min - Max	** - **	** - **	** - **

**Table 7: Tumour Characteristics at Baseline**

Data set: All Randomized Patients			
	Number of patients (%)		
	RT+BSC N=**	BSC N=**	Total N=**
Months from Initial Diagnosis to Randomization			
N	**	**	**
Median	**	**	**
Min - Max	** - **	** - **	** - **
Method of Initial Diagnosis			
Histology	** (**)	** (**)	** (**)
Cytology	** (**)	** (**)	** (**)
Standard Imaging Criteria	** (**)	** (**)	** (**)
Type of Liver Cancer			
HCC	** (**)	** (**)	** (**)
Liver Metastases	** (**)	** (**)	** (**)
Primary Tumour Type of Liver Metastases			
Type #1	** (**)	** (**)	** (**)
Type #2	** (**)	** (**)	** (**)
...	** (**)	** (**)	** (**)
Months From Liver Metastases Diagnosis to Randomization			
N	**	**	**
Median	**	**	**
Min - Max	** - **	** - **	** - **
Presence of Extrahepatic Cancer			
Yes	** (**)	** (**)	** (**)
No	** (**)	** (**)	** (**)
Primary in Place for Extrahepatic Cancer			
Yes	** (**)	** (**)	** (**)
No	** (**)	** (**)	** (**)
Site of Metastases 			
Bone	** (**)	** (**)	** (**)
Abdominal (outside the liver)	** (**)	** (**)	** (**)
Lung	** (**)	** (**)	** (**)
Brain	** (**)	** (**)	** (**)
Other	** (**)	** (**)	** (**)
Portal Vein or Other Vascular Invasion			
Yes	** (**)	** (**)	** (**)
No	** (**)	** (**)	** (**)
Other Liver Disease			
Yes	** (**)	** (**)	** (**)
No	** (**)	** (**)	** (**)
Type of Other Liver Disease 			
Hepatitis B	** (**)	** (**)	** (**)
Hepatitis C	** (**)	** (**)	** (**)
Cirrhosis	** (**)	** (**)	** (**)
Other	** (**)	** (**)	** (**)

Extent of Liver Metastases			
Diffuse	** (**)	** (**)	** (**)
Multifocal	** (**)	** (**)	** (**)
Locally Advanced	** (**)	** (**)	** (**)
Child-Pugh Class			
A	** (**)	** (**)	** (**)
B	** (**)	** (**)	** (**)
C	** (**)	** (**)	** (**)
Child-Pugh Score			
5	** (**)	** (**)	** (**)
6	** (**)	** (**)	** (**)
7	** (**)	** (**)	** (**)
8	** (**)	** (**)	** (**)
9	** (**)	** (**)	** (**)
10	** (**)	** (**)	** (**)
11	** (**)	** (**)	** (**)
12	** (**)	** (**)	** (**)
13	** (**)	** (**)	** (**)
14	** (**)	** (**)	** (**)
15	** (**)	** (**)	** (**)

 Patient may have more than one site of metastases

 Patient may have more than one other liver disease

**Table 8: Prior Surgery**

Data set: All Randomized Patients			
	Number of patients (%)		
	RT+BSC N=**	BSC N=**	Total N=**
Prior surgical/diagnostic procedure			
No	** (**)	** (**)	** (**)
Yes	** (**)	** (**)	** (**)
Procedure / Site			
Procedure / Site 1	** (**)	** (**)	** (**)
Procedure / Site 2	** (**)	** (**)	** (**)
....	*** (**)	*** (**)	*** (**)

**Table 9: Prior Radiotherapy**

Data set: All Randomized Patients			
	Number of patients (%)		
	RT+BSC N=**	BSC N=**	Total N=**
Any Prior Radiotherapy			
No	** (**)	** (**)	** (**)
Yes	** (**)	** (**)	** (**)
Site of Prior Radiotherapy 			
Site #1	** (**)	** (**)	** (**)
Site #2	** (**)	** (**)	** (**)
Site #3	** (**)	** (**)	** (**)
....	** (**)	** (**)	** (**)
Total Dose of radiotherapy (cGy)			
N	**	**	**
Median	**	**	**
Min - Max	** - **	** - **	** - **

 Patient may have more than one site of radiotherapy

**Table 10: Prior Systemic Therapy**

Data set: All Randomized Patients			
	Number of patients (%)		
	RT+BSC N=**	BSC N=**	Total N=**
Any Prior Systemic Therapy			
No	** (**)	** (**)	** (**)
Yes	** (**)	** (**)	** (**)
Drug / Agent Name 			
Drug #1	** (**)	** (**)	** (**)
Drug #2	** (**)	** (**)	** (**)
Drug #3	** (**)	** (**)	** (**)
...	** (**)	** (**)	** (**)

 Patient may have more than one drug of prior systemic therapy

**Table 11: Prior Regional Therapy**

Data set: All Randomized Patients			
	Number of patients (%)		
	RT+BSC N=**	BSC N=**	Total N=**
Any Prior Regional Therapy			
No	** (**)	** (**)	** (**)
Yes	** (**)	** (**)	** (**)
Therapy Name 			
TACE-DEB	** (**)	** (**)	** (**)
TACE-DEBIRI	** (**)	** (**)	** (**)
TAE-DEB	** (**)	** (**)	** (**)
TAE-DEBIRI	** (**)	** (**)	** (**)
Hepatic arterial chemotherapy	** (**)	** (**)	** (**)
Y90	** (**)	** (**)	** (**)
Other	** (**)	** (**)	** (**)

 Patient may have more than one therapy of prior regional therapy

**Table 12: Baseline Grade 2 or Higher Adverse Events**

Data set: All Randomized Patients									
	Number of patients (%)								
	RT+BSC N=**			BSC N=**			Total N=**		
	Grade			Grade			Grade		
	2	3	4	2	3	4	2	3	4
Patients with any AE	** (**)	** (**)	** (**)	** (**)	** (**)	** (**)	** (**)	** (**)	** (**)
Patients with AE within category	**(**)	**(**)	**(**)	**(**)	**(**)	**(**)	**(**)	**(**)	**(**)
Category 1 	**(**)	**(**)	**(**)	**(**)	**(**)	**(**)	**(**)	**(**)	**(**)
Event 1	**(**)	**(**)	**(**)	**(**)	**(**)	**(**)	**(**)	**(**)	**(**)
Event 2	**(**)	**(**)	**(**)	**(**)	**(**)	**(**)	**(**)	**(**)	**(**)
Event 3	**(**)	**(**)	**(**)	**(**)	**(**)	**(**)	**(**)	**(**)	**(**)
...	**(**)	**(**)	**(**)	**(**)	**(**)	**(**)	**(**)	**(**)	**(**)
Category 2 	**(**)	**(**)	**(**)	**(**)	**(**)	**(**)	**(**)	**(**)	**(**)
Event 1	**(**)	**(**)	**(**)	**(**)	**(**)	**(**)	**(**)	**(**)	**(**)
...	**(**)	**(**)	**(**)	**(**)	**(**)	**(**)	**(**)	**(**)	**(**)

(1) Patients may have more than one event within a category.

**Table 13: Baseline Hematology**

Data set: All Randomized Patients									
	Number of Patients (%)								
	RT+BSC N = **			BSC N = **			Total N=**		
	2	3	4	2	3	4	2	3	4
Hemoglobin									
Grade 0	** (**)			** (**)			** (**)		
Grade 1	** (**)			** (**)			** (**)		
Grade 2	** (**)			** (**)			** (**)		
Grade 3	** (**)			** (**)			** (**)		
Grade 4	** (**)			** (**)			** (**)		
Not reported 	** (**)			** (**)			** (**)		
Platelet									
Grade 0	** (**)			** (**)			** (**)		
Grade 1	** (**)			** (**)			** (**)		
Grade 2	** (**)			** (**)			** (**)		
Grade 3	** (**)			** (**)			** (**)		
Grade 4	** (**)			** (**)			** (**)		
Not reported 	** (**)			** (**)			** (**)		
Absolute Neutrophil Count									
Grade 0	** (**)			** (**)			** (**)		
Grade 1	** (**)			** (**)			** (**)		
Grade 2	** (**)			** (**)			** (**)		
Grade 3	** (**)			** (**)			** (**)		
Grade 4	** (**)			** (**)			** (**)		
Not reported 	** (**)			** (**)			** (**)		

(1) Not done or outside the 14-day window prior to randomization

**Table 14: Baseline Chemistry**

		Data set: All Randomized Patients		
		RT+BSC N = **	BSC N = **	Total N=**
Total bilirubin				
Grade 0	** (**)	** (**)	** (**)	** (**)
Grade 1	** (**)	** (**)	** (**)	** (**)
Grade 2	** (**)	** (**)	** (**)	** (**)
Grade 3	** (**)	** (**)	** (**)	** (**)
Grade 4	** (**)	** (**)	** (**)	** (**)
Not reported 	** (**)	** (**)	** (**)	** (**)
Alkaline phosphatase				
Grade 0	** (**)	** (**)	** (**)	** (**)
Grade 1	** (**)	** (**)	** (**)	** (**)
Grade 2	** (**)	** (**)	** (**)	** (**)
Grade 3	** (**)	** (**)	** (**)	** (**)
Grade 4	** (**)	** (**)	** (**)	** (**)
Not reported 	** (**)	** (**)	** (**)	** (**)
ALT				
Grade 0	** (**)	** (**)	** (**)	** (**)
Grade 1	** (**)	** (**)	** (**)	** (**)
Grade 2	** (**)	** (**)	** (**)	** (**)
Grade 3	** (**)	** (**)	** (**)	** (**)
Grade 4	** (**)	** (**)	** (**)	** (**)
Not reported 	** (**)	** (**)	** (**)	** (**)
AST				
Grade 0	** (**)	** (**)	** (**)	** (**)
Grade 1	** (**)	** (**)	** (**)	** (**)
Grade 2	** (**)	** (**)	** (**)	** (**)
Grade 3	** (**)	** (**)	** (**)	** (**)
Grade 4	** (**)	** (**)	** (**)	** (**)
Not reported 	** (**)	** (**)	** (**)	** (**)
Albumin				
Grade 0	** (**)	** (**)	** (**)	** (**)
Grade 1	** (**)	** (**)	** (**)	** (**)
Grade 2	** (**)	** (**)	** (**)	** (**)
Grade 3	** (**)	** (**)	** (**)	** (**)
Grade 4	** (**)	** (**)	** (**)	** (**)
Not reported 	** (**)	** (**)	** (**)	** (**)
Serum Creatinine				
Grade 0	** (**)	** (**)	** (**)	** (**)
Grade 1	** (**)	** (**)	** (**)	** (**)
Grade 2	** (**)	** (**)	** (**)	** (**)
Grade 3	** (**)	** (**)	** (**)	** (**)
Grade 4	** (**)	** (**)	** (**)	** (**)
Not reported 	** (**)	** (**)	** (**)	** (**)
Alpha-Fetoprotein				
Normal	** (**)	** (**)	** (**)	** (**)
High 	** (**)	** (**)	** (**)	** (**)
Not reported 	** (**)	** (**)	** (**)	** (**)

(1) Not done or outside the 14-day window prior to start of randomization

(2) High than upper lower limit

